After the run-in phase, patients will be admitted for up to 5 days, for the initial biopsies and extended tests as detailed above. At the LDB, it is our standard practice to keep all patients for observation overnight after a biopsy, and to perform a routine complete blood count 6 hours after the procedure. Following discharge, patients will be seen in the

outpatient clinic for the first 3 weeks of treatment, and will be subsequently admitted during the 4th week of treatment, for the second biopsy. At this stage, visits that are within 2 days before or after the scheduled visit date will not be considered a protocol violation. Following the second admission, the patients will be followed in clinic every 4 weeks. From this time point onwards, visits that are within 1 week before or after the planned visit date will not be considered a protocol violation. Patients will be admitted again at the end of the 24 week period for another extensive evaluation. During the extended treatment phase, patients will be seen every 12 weeks.

Patients will also be monitored as appropriate for patients with liver disease. Specifically, patients with liver cirrhosis or high-risk for hepatocellular carcinoma (HCC) will undergo surveillance for HCC by ultrasound or cross sectional imaging every 6-12 months, or according to most current guidelines. Patients with cirrhosis will be monitored by endoscopy as appropriate for the development of esophageal varices.

Patients who become pregnant during the study will be withdrawn, as pregnancy and associated hormonal and metabolic changes may affect hepatic fat metabolism and will confound the analysis. Patients who do not respond to treatment by week 48 will be withdrawn for futility. There are no other pre-specified criteria for withdrawal of patients from the study. Patients will be withdrawn if, according to the best judgment of the treating physician or the principal investigator, continuing treatment poses an unacceptable risk to the patient.

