⁵ NK/NKT cell analyses – On Run-in phase, first admission and week 144 will be drawn for all patients. On weeks 4 and 24 these will be performed only on the 200 IU/d and 800 IU/d arms (total volume 48 ml). On week 144 only 30 ml will be obtained. Will not be performed if Hb < 10 g/dL.

⁶ FSIVGTT – total blood volume drawn 120-150 ml. Will not be performed if Hb < 10 g/dL.

⁷ Possible lowering of vitamin E dose based on week 48 results (see Figure 4).

Analysis of the study

End points

Primary end points

There are two primary clinical end points in the study. The primary biochemical response is defined in a binary manner as an end-of-treatment AST <=32 or ALT <=35 U/L. The selection of these cut-off values is based on a pilot analysis by us that examined in an unbiased manner several rules for biochemical response and found this to be the one most strongly associated with histological response to treatment, irrespective of treatment modality³¹. We will also analyze the absolute change in ALT and AST from pre-treatment to end-of treatment as continuous parameters of the effect of treatment on liver enzymes. Patients who at the time of starting vitamin E treatment have normal liver enzymes will be excluded from this analysis. The primary physiological response is the absolute change in liver fat content as determined by comparing the ¹H-MRS results from pre-treatment to end of treatment.

Secondary end points

Secondary end points include: absolute and percent decrease in liver enzymes, decrease in GGT levels, percent reduction in liver fat.

A secondary analysis will analyze the effect of the lifestyle modification by comparing the end points between enrollment and the end of the lifestyle modification phase. Another analysis will determine the effect of increasing the dose of vitamin E by comparing the end points between the end of the randomized phase (week 24) to weeks 24 and 144 of the extended phase.

The kinetics of response will be determined by analyzing sequential ALT and AST measurements. Current data suggest biphasic response pattern to vitamin E and mathematical modeling will be applied to the results and will be compared between doses. Similar modeling will be applied to changes in liver fat content by ¹H-MRS.

Basic scientific end points

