For the comparison of effectiveness between different doses of vitamin E (primary aim 1), the primary biochemical end point will be used. We assume a response rate of 45% with the 800 IU/d dose (similar to that seen at the PIVENS trial), a 10% response rate to the 200 mg/d dose and a 20% response to the 400 mg/d dose. Under these assumptions, a sample size of 25 patients per group will give a power of 80% to detect a linear trend with statistical significance of 5% (Cochran-Armitage test). To account for possible drop-out and loss to follow-up, we are aiming to recruit 30 patients per group or an overall of 90 patients in the study.

As the sample size calculation is limited by the absence of published data, we will re-assess our calculations after 10 patients have been enrolled in each arm, and again after 20 have been enrolled

Human subject protections

Rationale for subject selection

The study is designed to enroll patients with NAFLD that can be potentially benefit from treatment. Currently, there are no reliable non-invasive markers that accurately distinguish NASH from steatosis only, although the latter seems to carry a more favorable prognosis. For patients with steatosis only, it is unclear whether treatment can improve their disease and prevent progression to NASH. In most clinical trials with histological end points, patients with steatosis only were excluded as they cannot show significant histological

improvement. In this study, with a primarily scientific outcome, we are interested in studying the effect of vitamin E on these patients as well and we consider the intervention to be low-risk enough to allow us to recruit all patients with NAFLD.

The exclusion criteria for the study are mainly geared towards limiting enrollment to patients for whom treatment is considered safe and that have no confounders that would limit the analysis of the results. There are no limitations based on race or ethnicity. However, we anticipate that very few patients of African ancestry will be enrolled, because of the scarcity of NAFLD in these patients and their apparent "protection" from liver fat accumulation.

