As some studies suggest an effect of vitamin E on platelet aggregation⁴², and given the possible association with hemorrhagic stroke, we exclude patients with high bleeding risk, such as those with coagulopathies, use of anticoagulants, thrombocytopenia or known platelet dysfunction. Furthermore, due to the possibility of increased risk of gastrointestinal bleeding, patients with a pre-existing history of iron deficiency anemia secondary to gastrointestinal sources are excluded. On the other hand, vitamin E supplementation is not associated with changes in standard parameters of bleeding tendency, including PT, PTT,

platelet count and bleeding time^{43, 44}, rendering these useless as a tool for safety monitoring during vitamin E treatment. However, if during the study the platelet count or PT/PTT cross the thresholds for study inclusion (i.e. platelets <70,000, PT/PTT prolonged by >=3 seconds), treatment will be stopped and patients withdrawn from the study.

Recently, data from extended follow-up of the SELECT trial⁴⁵ suggested increased risk for the diagnosis of prostate cancer in patients treated with vitamin E. This is in contrast to the findings of two other similar studies^{46, 47} which did not show such an effect. Our patients are anticipated to be significantly younger than the study population in SELECT (median age 62); furthermore, risk for prostate cancer appeared to increase numerically only after more than 3 years of treatment. We will monitor PSA levels every 12 months on male patients in our study. Screening for prostate cancer may lead to further evaluation of abnormal results, including referrals, blood tests and possible invasive procedures. There is also a risk of detecting prostate cancers that are not destined to become clinically significant. The risks and benefits of screening with annual PSA testing will be discussed with all male participants prior to enrollment and patients will have the option to elect not to be screened.

Adverse event reporting and data monitoring

Reportable events will be tracked and submitted to the IRB as outlined in Policy 801.

The PI will immediately report SAEs to the Sponsor according to the requirements of 21 CFR 312.64(b) and as agreed upon with the sponsor. The PI will record nonserious AEs and report them to the Sponsor according to the timetable for reporting specified in the protocol (21 CFR 312.64(b).

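### Two stopping rules end study participation as well as vitamin E, with no week-24 assessment and no missing-data rule, so the resulting loss of both primary end points may be informative

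*Combined protocol and SAP*

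**What the plan says.** Withdrawal is described in two places.

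- **Monitoring subjects and criteria for withdrawal of subject from the study.** Three grounds are given. For pregnancy: "Patients who become pregnant during the study will be withdrawn". For futility: "Patients who do not respond to treatment by week 48 will be withdrawn for futility". For clinical judgment: "Patients will be withdrawn if, according to the best judgment of the treating physician or the principal investigator, continuing treatment poses an unacceptable risk". The section also states: "There are no other pre-specified criteria for withdrawal of patients from the study".
- **Risks and Discomforts, Vitamin E treatment.** If the platelet count or PT/PTT crosses the inclusion threshold during the study, "treatment will be stopped and patients withdrawn from the study".

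The end points are set under Primary end points. "The primary biochemical response is defined in a binary manner as an end-of-treatment AST <=32 or ALT <=35 U/L". The second is the absolute change in MRS liver fat from pre-treatment to end of treatment. For a patient who completes the randomized phase, both come from the week-24 admission (Vitamin E Treatment; Table 1).

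Before that admission, Chem-20 is drawn at weeks 1, 2, 3, 4, 8, 12, 16 and 20, and MRS is repeated once, at week 4. Table 1 has no early-termination visit and no visit for patients off vitamin E. Statistical analyses plans matched-pair comparisons and a Cochran-Armitage trend test, but names no analysis population and no rule for missing values.

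Sample size calculation allows for loss without giving reasons or a rate: "To account for possible drop-out and loss to follow-up, we are aiming to recruit 30 patients per group".

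**The concern.** Whether vitamin E is safe to continue and whether a patient can still be measured are separate questions. The two rules answer both at once. A patient who crosses a laboratory threshold at week 10 may be willing to return at week 24 for a blood draw and an MRS, neither of which is invasive. As written, the plan does not ask. The data are lost by design, not by refusal.

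The stake is the dose comparison. If patients who leave differ in response from those who stay, and leave at different rates by dose, an analysis of completers no longer compares the randomized groups. The physician-judgment rule is where this could most plausibly happen: its criterion is open-ended, the documents describe no masking of the randomized phase, and capsule strength and number differ by arm. The Introduction also raises bleeding risk as a dosing issue, and a secondary aim asks about a dose response in the anti-platelet effect.

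**Working it through.** **1. Can the rules act before week 24?** Yes. Blood counts are taken throughout the randomized phase, PT/PTT is among the extended labs at weeks 4 and 12 (Table 1), and clinical judgment can apply at any time. The futility rule acts at week 48, after the week-24 end points, and is not part of this point.

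**2. What remains for a patient withdrawn at week 10?** ALT/AST through week 8 and an MRS at week 4. The week-24 values are absent. The week-4 MRS is a poor substitute: the section Liver biopsies says no marked fall in liver fat is expected in those 4 weeks. No text says whether a last on-treatment value may count as end of treatment.

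**3. The plan's own sample size.** Inputs from Sample size calculation: response 10%, 20% and 45%; 25 per group; 5% significance; Cochran-Armitage test. Assumed: two-sided, scores 1-2-3 (centred -1, 0, 1), no continuity correction.

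- Mean rate = (0.10 + 0.20 + 0.45)/3 = 0.25
- Expected trend statistic = 25 × (0.45 − 0.10) = 8.75
- Null SD = √(25 × 0.25 × 0.75 × 2) = √9.375 = 3.062
- Alternative SD = √(25 × (0.10 × 0.90 + 0.45 × 0.55)) = √8.4375 = 2.905
- Power = Φ((8.75 − 1.96 × 3.062)/2.905) = Φ(0.946) = 82.8%

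With scores 200-400-800 it is 83.8%; with a continuity correction the figures are 78.1% and 81.0%. The stated 80% at 25 per group is reproduced. The dropout allowance is 5/30 = 16.7%, since 25/(1 − 1/6) = 30.

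**4. Bounds on the 800-minus-200 difference.** Completers respond at the planned rates, and lost patients are set to all non-responders or all responders.

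| Lost per arm | 800 IU/d, of 30 | 200 IU/d, of 30 | Difference |
|---|---|---|---|
| 5 (whole allowance) | 11.25/30 = 37.5% to 16.25/30 = 54.2% | 2.5/30 = 8.3% to 7.5/30 = 25.0% | 37.5 − 25.0 = 12.5 to 54.2 − 8.3 = 45.8 |
| 1 (assumption) | 13.05/30 = 43.5% to 14.05/30 = 46.8% | 2.9/30 = 9.7% to 3.9/30 = 13.0% | 43.5 − 13.0 = 30.5 to 46.8 − 9.7 = 37.2 (unrounded inputs) |

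The completer difference is 45 − 10 = 35 points. Fractional patients arise from applying rates to small groups; the bounds are indicative.

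**5. What selective loss could do to the trend test.** Assumed scenarios: 30 per arm, loss only from the 800 arm, completers analysed, two-sided 5%, full binomial enumeration. Results are for scores 1-2-3 / 200-400-800.

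- Planned effect, no loss: power 90.3% / 90.7%.
- Planned effect, 5 responders lost (800 rate becomes 8.5/25 = 34%): 61.6% / 59.7%.
- Planned effect, 5 non-responders lost (13.5/25 = 54%): 96.3% / 97.1%.
- No dose effect, 25% in every arm, 5 non-responders lost (7.5/25 = 30%): rejection 6.8% / 7.9%. With 3 lost: 6.3% / 6.1%.

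These show how the analysis would react, not what will happen.

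**The case against.** A reader might infer four stronger things. The documents do not support them.

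- **That every early stop means leaving the study.** The rules cover named triggers. Stopping by choice or for tolerability is not addressed either way.
- **That early stoppers have no measurement of either end point variable.** Enzymes are drawn at eight visits before week 24 and MRS is repeated at week 4. What is missing is the planned week-24 value.
- **That loss will be selective by dose.** No withdrawal rates by dose or response are given. Immediately before the laboratory rule, the protocol says vitamin E does not alter PT, PTT, platelet count or bleeding time, so by its own account that trigger should not track dose. It also reports no excess adverse events on vitamin E over placebo in the adult trial it cites, which used 800 IU. The dose concern in the Introduction is hemorrhagic stroke, and the secondary aim concerns an anti-platelet effect; neither says these laboratory values change with dose.
- **That 12.5 to 45.8 points measures this problem.** It charges the entire allowance for drop-out and loss to follow-up to these two rules and takes opposite extremes in the two arms. Patients truly lost to follow-up would stay missing under any fix.

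It is also fair to say that, in a phase IIa study mainly about mechanism, an on-treatment dose response is a legitimate target. A week-24 value from a patient who stopped at week 10 follows 14 weeks off drug. Which analysis leads is a choice to be stated, not an error to be corrected.

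These objections narrow the point without removing it. The two rules do end participation, and no provision recovers the week-24 values or says how their absence is handled. The protocol keeps patients in elsewhere: low hemoglobin cancels the second or third biopsy but not participation, and declining the extension is not an exclusion.

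**Conclusion.** The point holds for the two named rules. A patient withdrawn under them before week 24 loses the planned week-24 value of both primary end points, and the plan neither seeks that value nor handles its absence. The loss may be informative. Dose-related loss is a risk, chiefly through the physician-judgment rule, and is not demonstrated.

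The size is unknown because no withdrawal rate is given. Against a 35-point completer difference, the bounds are about 30.5 to 37.2 points if one patient per arm is lost this way, and 12.5 to 45.8 in the worst case of 5 per arm. Both rest on the plan's assumed response rates holding among completers. Patients with normal enzymes at the start of vitamin E are excluded from the biochemical analysis, so its denominators will be smaller and each lost patient will weigh more.

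Separately, the withdrawal section says its list is complete, while the risk section adds the platelet and PT/PTT criterion. These passages contradict each other and must be reconciled. The change is worth making because it is cheap and reduces a possible bias; the documents do not show that the trial is compromised without it.

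**What to change.** Leave the stopping rules as they are and change only what follows them.

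1. In the withdrawal section and in the vitamin E risk section, separate stopping vitamin E from leaving the study. A patient who stops before week 24 stays in follow-up unless consent is withdrawn, and attends the week-24 visit for AST/ALT, weight and MRS, with no biopsy. Exempt patients who stop because of pregnancy. Say that this also covers stopping by choice or for tolerability.
2. Add the visit as a footnote to Table 1.
3. In Statistical analyses, report the dose comparison by randomized arm including these week-24 values, alongside the on-treatment analysis. State in advance which leads, what end of treatment means for an early stopper, and how values still missing are handled.
4. Reconcile the statement that no other withdrawal criteria exist with the platelet and PT/PTT rule.

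The cost is some protocol wording and, for each patient concerned, one blood draw and one MRS already on the schedule. The downside is that some week-24 values will reflect time off drug, which may dilute the estimated effect; the on-treatment analysis beside it lets the reader judge by how much.
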